6.3.11 Other Safety Assessments

Vital Signs

For vital signs parameters (systolic and diastolic blood pressure, supine heart rate and temperature) summary statistics will be produced for observed values by visit. In addition, the difference from baseline to each visit at which they were assessed will be derived and presented.

Vital signs assessed at time points post vaccination will be summarised separately.

Clinical Laboratory Measurements

The laboratory categories are Hematology, Clinical Chemistry, Coagulation, Urine analysis and Pregnancy analysis.

For all laboratory parameters, summary statistics will be produced for observed values by visit. In addition, the difference from baseline to each visit at which they were assessed will be derived and presented. The number of abnormal (low and high) and clinically significant observations will be tabulated for each treatment group by visit. Abnormal values will be flagged in listings.

Shift tables that show the number of patients who changed from low, normal or high at baseline to low, normal or high at each post-baseline time of assessment will be presented.

Physical Examination

Physical examination results will be tabulated including number of subjects with normal, abnormal not clinically significant or clinically significant abnormalities by visit. Corresponding shift tables for changes from baseline will be presented, and all the results will be listed.

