AEs	X	X ^c	X ^c	X	X	X	X	X ^k	X ^v	X
Diagnosis Confirmation ^f				X						

a Assessment to be completed before nephrectomy and may be done the day before nephrectomy for logistical reasons

Locally analyzed Creatinine for patients included in the study before 28 August 2017 (if performed as part of clinical routine) to be recorded in eCRF

b Height only at Screening. Weight at all visits except for Vacc1 and Vacc2 Visits.

c See specific flow chart, *Table 3*, for detailed instructions on pre- and post-vaccination assessments.

d Physical examination, ECOG performance, and samples for safety lab and urinalyses may be taken the day before vaccination for logistical reasons

Locally analyzed results for Hb, WBC, platelets, PT-INR, and APTT need to be available before vaccination

Locally analyzed results for Hb, WBC, and clinical chemistry might need to be available prior to nephrectomy

- Analysis of coagulation status at Nephrectomy is not necessary provided the patient is not on anticoagulant treatment. For patients on anticoagulants local sampling practice applies.
- e Pregnancy test in blood at Screening, and in either blood or urine at Vacc1 and Vacc2 Visits. The pregnancy test result is needed prior to each vaccination.
 - f Samples for auto- and alloimmunization analyses will be collected prior to vaccination at Vacc1 Visit. Sampling at Sun-Start Visit only applicable for patients randomized to Intuvax.
 - g To be done when the results from all assessments made are available. Telephone contact with patient to inform about treatment and timing of next study visit.
 - h The prescribed dose to be in accordance with the SmPC/USPI including any dose adjustments.
 - i Return of sunitinib not applicable at Sun-Start Visit and Distribution not applicable at End-of-Study Visit. Standard of Care applies after End-of-Study.
 - j Start of sunitinib administration will be dependent on wound healing. The time window for initiation is five (5) to eight (8) weeks after Nephrectomy.
 - k Post-study collection of survival data.
 - l If CT cannot be used for some reason, MRI is acceptable. The same modality has to be used at all visits.

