6.3.2 Summary Statistics

In general, data will be summarized by means of summary statistics. Continuous data will be presented with the number of observations, mean value, standard deviation, minimum, Q1, median, Q3 and maximum value. Categorical data will be presented as counts and percentages. All efficacy related variables will be summarized for the FAS population and all safety related data will be summarized for the safety population.

For any assessments being evaluated by visit, an LOCF (Last observation carry forward) approach will be applied, where the last available information will be combined, independently of what the last recorded visit is.

All descriptive statistics will be presented by stratum of high- and intermediate risk patients and pooled together and by treatment group.

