If the date of first and/or last dose of study drug administration is missing then duration of exposure will be set to missing.

Handling of unscheduled visits

Descriptive summaries and by-visit analyses will be presented according to the planned (scheduled) visits, unless otherwise specified.

For patients withdrawing early, where discontinuation data is collected on the end-of-trial visit, the data will be reallocated to the visit nearest to withdrawal, if applicable.

Any data collected on unscheduled visits, will be reallocated to the visit nearest in time to the planned visits where the corresponding information is not already available. This will be done by allocating the unscheduled data within the visit windows by corresponding visit as listed below.

Vacc1	from screening to 28 days
Vacc2	+/- 3 days
	At least 3 days after Vacc2 Visit and within 63 days from Screening Visit for patients randomized to Intuvax followed by sunitinib. Within 63 days from Screening Visit for patients randomized to sunitinib only.
Nephrectomy Visit:	
Sun-Start Visit:	Five (5) to eight (8) weeks after Nephrectomy Visit
SFU[6W]:	6 weeks (± 7 days) after Sun-Start Visit
SFU[12W]:	12 weeks (± 7 days) after Sun-Start Visit
SFU[24W]:	24 weeks (± 7 days) after Sun-Start Visit
SFU[36W]:	36 weeks (± 7 days) after Sun-Start Visit
SFU[48W]:	48 weeks (± 7 days) after Sun-Start Visit
SFU[60W]:	60 weeks (± 7 days) after Sun-Start Visit
End of Study Visit:	78 \pm 2 weeks after Screening

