14.3.1 Displays of Adverse Events

- 14.3.1.1 Summary of Adverse Events
- 14.3.1.2 Summary of Adverse Events by ilixadencel batch subgroup
- 14.3.1.3 Adverse Events by System Organ Class and Preferred term
- 14.3.1.4 Adverse Events: Number of Patients by Intensity and Relationship by Treatment
- 14.3.1.5 Adverse Events: Number of Patients by Intensity and Relationship by Treatment by ilixadencel batch subgroup
- 14.3.1.6 Serious Adverse Events by System Organ Class and Preferred term
- 14.3.1.7 Related Adverse Events by System Organ Class and Preferred term
- 14.3.1.8 Adverse Events by CTCAE grade and System Organ Class and Preferred term
- 14.3.1.9 Adverse Events occurring 4 hours following the Intuvax vaccination
- 14.3.1.10 Adverse Events occurring between first assessment at Screening and first Intuvax dose
- 14.3.1.11 Adverse Events occurring between first assessment at Screening and Nephrectomy
- 14.2.1.12 Related Serious Adverse Events by System Organ Class and Preferred term

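### On uninterrupted 4/2 dosing the SFU safety rows describe the end of the off-drug weeks, and SAP 6.6 keeps mid-cycle Extra Visit values out of them

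*SAP*

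**What the plan says.** Protocol 7.2.1.6 sets the SFU visits at weeks 6, 12, 24, 36, 48 and 60 after Sun-Start, each ±7 days, with laboratory tests and vital signs at every one. Protocol 7.2.1.5 starts sunitinib at the Sun-Start Visit. Protocol 9.1.5 names 4/2 (four weeks on, two off) as the standard schedule and allows 2/1 if side effects are unacceptable. Note h to Protocol Table 2 adds: "The prescribed dose to be in accordance with the SmPC/USPI including any dose adjustments". Protocol 7.2.1.9 provides symptom-driven Extra Visits, at which laboratory tests and vital signs are also taken.

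SAP 6.3.11 summarises both kinds of data by visit. For laboratory data: "The number of abnormal (low and high) and clinically significant observations will be tabulated for each treatment group by visit". Shift tables run from baseline "to low, normal or high at each post-baseline time of assessment".

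Under SAP 6.6 the rows are the planned visits. Unscheduled data are "reallocated to the visit nearest in time to the planned visits where the corresponding information is not already available", and this is done by "allocating the unscheduled data within the visit windows by corresponding visit as listed below". When a patient withdraws early, "the data will be reallocated to the visit nearest to withdrawal, if applicable". SAP 6.3.2 adds a last-observation rule for by-visit data, "where the last available information will be combined, independently of what the last recorded visit is".

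**The concern.** If the visit interval is a whole number of dosing cycles, every scheduled sample meets the patient at the same point of the cycle. Here that point is the end of the off-drug weeks. Extra Visits are the main source of values from the middle of the on-drug weeks, and SAP 6.6 gives those values no place in the SFU rows.

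Safety and tolerability is a secondary objective, and clinically significant laboratory and vital-sign changes belong to the safety endpoint. Nothing in the SAP tells someone reading the SFU rows which part of the cycle they describe. Nor would the tables show which entries came from another cycle day through withdrawal reallocation or the last-observation rule.

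**Working it through.** The plan gives no figure of its own on this point, so there is none to reproduce. The check is calendar arithmetic on the inputs above, with the first dose at Sun-Start as day offset 0.

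**1. Where the nominal visits fall.** The SFU offsets are 7 × 6, 12, 24, 36, 48, 60 = 42, 84, 168, 252, 336, 420 days.
- Divided by 42 (4/2): 1, 2, 4, 6, 8, 10, remainder 0 each time.
- Divided by 21 (2/1): 2, 4, 8, 12, 16, 20, remainder 0 each time.

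**2. What the windows cover.** On 4/2, cycle day = (offset mod 42) + 1, with days 1-28 on drug and 29-42 off.
- The seven days before a nominal visit are cycle days 36-42, all off drug.
- The nominal day and the seven after it are cycle days 1-8.
- Six windows × 15 days = 90 days: 6 × 7 = 42 off drug and 6 × 8 = 48 on drug.
- The 48 is an upper limit. Protocol 9.1.4 dispenses drug to last until the next planned visit, so a late attender may not have restarted.

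**3. What the windows miss.**
- 4/2: days 9-28 are 20 per cycle; 10 × 20 = 200 of 420 days (47.6%), and 0 of 90 window days.
- Aligned 2/1: days 9-14 are 6 per cycle; 20 × 6 = 120 of 420 days (28.6%), and again 0 of 90.

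**4. Applying SAP 6.6.** An Extra Visit value enters a planned row only if that row has no value and the date lies in the row's window. A value from cycle days 9-28 fails the second test for every SFU row, even when the SFU value is missing.

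**5. Whether another summary uses the values.** SAP 6.3.11 and Appendix 1, sections 14.3.4 and 14.3.6, list by-visit summaries, shift tables and post-vaccination vital signs. They list no worst-value or worst-grade table. Some on-drug values can still reach a table:
- through the End-of-Study row, which is timed from Screening and not tied to the cycle, or by filling a missing Sun-Start or End-of-Study value;
- through withdrawal reallocation, for which no window is stated;
- through the loosely worded last-observation rule;
- possibly through the shift tables, if each time of assessment is taken literally.

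**6. How far the alignment extends.**
- *Change from 4/2 to 2/1.* Let 2/1 start on day s (1-42) of a 4/2 cycle and run uninterrupted. The cycle day at the next nominal SFU visit is ((42 − (s − 1)) mod 21) + 1. This equals 1 only for s = 1 and 22 (2 of 42). It falls in days 9-14 for s = 9-14 and 30-35 (12 of 42). The window touches at least one of days 9-14 for 40 of 42 values of s.
- *Week 60.* Nephrectomy by day 63 (9 weeks) plus 8 weeks puts Sun-Start as late as week 17. Then 17 + 60 = 77, and from week 76 on SFU[60W] counts as the End-of-Study Visit. With five SFU visits the windows total 5 × 15 = 75 days, still with none in cycle days 9-28.

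**The case against.** The strongest reply is that counting days is not counting missed abnormalities. The timing matters only if values differ between on-drug and off-drug weeks, and the documents do not say how they differ. This stands. A reader might infer that the SFU rows understate sunitinib toxicity, but neither document supports a direction or a size.

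A reader might also infer that the mid-cycle values are lost. They are not. Appendix 1 plans listings of individual laboratory measurements, abnormal values, vital signs and visit dates, and SAP 6.3.3 allows dates and relative days in listings. Under Protocol 11.2 a clinically significant asymptomatic value is an adverse event; where symptoms accompany an abnormal value, the symptom is the event and the value is supporting information. Appendix 1 includes a table titled "Adverse Events by CTCAE grade and System Organ Class and Preferred term". What no planned summary is built to show is therefore mainly the asymptomatic values not judged clinically significant, and the values behind symptoms that were coded as events.

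The alignment is also least secure in patients who tolerate sunitinib badly, since they are the ones switched to 2/1 or dose-adjusted. This stands, and it limits the point to uninterrupted dosing. Finally, the cause is the visit schedule and by-visit tables follow Protocol 12.1.13. That is true, but SAP 6.6 decides what happens to Extra Visit values already collected, and that can still be changed.

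**Conclusion.** The point holds for patients on the version 4.0 or later schedule who take uninterrupted 4/2, or 2/1 aligned from Sun-Start. For them each nominal SFU visit ends an off-drug period, no SFU window contains a cycle day from 9 to the end of the on-drug weeks, and SAP 6.6 bars Extra Visit values from those days from the SFU rows. It does not cover intermediate-risk patients from before version 4.0, who under SAP 4.1 started sunitinib only after confirmed progression. It does not describe all six visits in every patient either: follow-up visits stop at progression and SFU[60W] may be the End-of-Study Visit.

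The effect on any tabulated value cannot be estimated. The documents do not give the number of Extra Visits, the number of schedule changes, or the on-drug to off-drug difference. Both arms share the SFU schedule, so the timing does not in itself bias the comparison between them. The tables are descriptive and the survival analyses are untouched. This is a low-priority improvement in safety reporting.

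**What to change.** In SAP 6.3.11 and Appendix 1, sections 14.3.4 and 14.3.6, add one descriptive table per arm of each patient's worst post-Sun-Start value for platelets, neutrophils, haemoglobin, liver tests and blood pressure. Use the CTCAE grade where it can be derived from the recorded value, otherwise low, normal or high; for blood pressure the SAP would have to state the cut-offs, since Protocol 10.5.4 gives none. Include all recorded values, Extra Visits and End-of-Study among them, regardless of the SAP 6.6 windows, and show the number of values per patient.

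Add one sentence to the SAP and the study report: scheduled SFU values are nominally end-of-off-period values, and withdrawal reallocation and the last-observation rule can mix in other cycle days.

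The cost is one table and one sentence, with no new visits or samples. Grading raw values is a small new derivation, because the protocol applies CTCAE to adverse events. Extra Visit values are symptom-driven in an open-label trial, so the table is descriptive only. It adds the Extra Visit values but cannot recover on-drug days that were never sampled.

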6.4 Level of Significance, Multiple Comparisons and Multiplicity

The sample size in this trial is not based on a formal power calculation. Any inferential statistical methods applied in this trial will be regarded as exploratory, therefore no adjustments will be applied to adjust for multiple testing.

6.5 Adjustment for Covariates

Parametric analyses based on statistical models will not be conducted. For primary endpoint a stratified Log-rank test will be done including adjustment for high/intermediate risk strata.

6.6 Handling of Dropouts and Missing Data

Primary and secondary efficacy endpoint

The primary and secondary efficacy endpoint analysis will be conducted on available data (observed cases). Missing data due to loss of follow-up and rules for censoring will be done as described in each corresponding section.

Handling of incomplete dates

Incomplete (partial or missing) dates will be presented in data listings as provided on the eCRF. However, for use in calculations (e.g. to calculate the duration of an AE or medication use) dates will be estimated as follows.

For partial start-dates

- If the year is unknown, then the date will not be imputed and will be assigned a missing value
- If the month is unknown, then:
 - If the year matches the year of the first dose date, then impute the month and day of the first dose date
 - Otherwise, assign 'January'
- If the day is unknown, then:
 - If the month and year match the month and year of the first dose date, then impute the day of the first dose date.
 - Otherwise, assign 'January'.

For partial end-dates,

- If the year is unknown, then the date will not be imputed and will be assigned a missing value.
- If the month is unknown, then assign 'December'.
- If the day is unknown, then assign the last day of the month

If the above rules for end-dates result in a date after the patient was ended the study, then the end date will be replaced with the patient's date of completion/withdrawal. Furthermore, should the above rules not result in the most conservative date (as described below), then the imputed value may be replaced by a date that will lead to a more conservative analysis.

After implementing the rules above, to determine whether AEs with incomplete start or stop dates are pre-treatment or treatment-emergent the following strategy will be used:

- If the start date and stop date are both missing, the most conservative approach is taken and the AE is considered to be treatment-emergent
- If the start date is missing but the stop date is not missing and is on or after the day of first study drug administration but before or on the Week 12 visit date then the most conservative approach is taken and the AE is considered to be treatment-emergent;
- If the start date is missing but the stop date is not missing and is before the day of first study drug administration then the AE is considered to be pre-treatment.

If the date of first and/or last dose of study drug administration is missing then duration of exposure will be set to missing.

Handling of unscheduled visits

Descriptive summaries and by-visit analyses will be presented according to the planned (scheduled) visits, unless otherwise specified.

For patients withdrawing early, where discontinuation data is collected on the end-of-trial visit, the data will be reallocated to the visit nearest to withdrawal, if applicable.

Any data collected on unscheduled visits, will be reallocated to the visit nearest in time to the planned visits where the corresponding information is not already available. This will be done by allocating the unscheduled data within the visit windows by corresponding visit as listed below.

Vacc1	from screening to 28 days
Vacc2	+/- 3 days
	At least 3 days after Vacc2 Visit and within 63 days from Screening Visit for patients randomized to Intuvax followed by sunitinib. Within 63 days from Screening Visit for patients randomized to sunitinib only.
Nephrectomy Visit:	
Sun-Start Visit:	Five (5) to eight (8) weeks after Nephrectomy Visit
SFU[6W]:	6 weeks (± 7 days) after Sun-Start Visit
SFU[12W]:	12 weeks (± 7 days) after Sun-Start Visit
SFU[24W]:	24 weeks (± 7 days) after Sun-Start Visit
SFU[36W]:	36 weeks (± 7 days) after Sun-Start Visit
SFU[48W]:	48 weeks (± 7 days) after Sun-Start Visit
SFU[60W]:	60 weeks (± 7 days) after Sun-Start Visit
End of Study Visit:	78 \pm 2 weeks after Screening

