As the technology used by [REDACTED] eliminates much more the subjective measurement of CD8+ infiltration and has been technically validated, the [REDACTED] approach is widely regarded as the more accepted one in contrast to the [REDACTED] approach. Additionally, issues in the quality of the execution had been identified in the beginning of the

[REDACTED]

[REDACTED]

[REDACTED]

Evaluation of auto- and allo-immunization parameters

Auto- and alloimmunization parameters will be assessed prior to vaccination at Vacc1 Visit and at Sun-Start Visit for patients randomized to Intuvax.

Autoimmunization parameters, anti-nuclear antibodies (IF-ANA), anti-mitochondrial and anti-liver-kidney icrosomal antigens will be assessed as “Negative” or “Positive” and additional assessment of “Weak” or “Strong” will be done for positive results on Homogenous, Speckled, Nucleolar, and Centromere patterns.

Alloimmunization at the humoral level by screening of alloantibodies against HLA-A, B, C (HLA class I) and HLADR, DQ, DP (HLA class II) antigens will be assessed as “Present” or “Not Present”.

The results of auto- and allo-immunization parameters will be tabulated using general summary statistics for categorical data. In addition shift tables will be presented to summarise the changes from the assessment prior to vaccination 1, to the Sun-start visit.

TTF defined as progressing during or after treatment with Intuvax+sunitinib or sunitinib followed by the start of subsequent second line systemic therapy

TTF is defined as progressing during or after treatment with Sunitinib or Intuvax + Sunitinib followed by the start of subsequent second line systemic therapy including immune checkpoint inhibition or tyrosine kinase inhibition, and will be derived as the date of screening until start date of second line treatment following progression. Similar censoring rules as applied for PFS will be used. Patients with PD without any second line treatment will be censored at withdrawal. Similar survival statistics as applied for analysis of PFS will be conducted.

Association between Sunitinib dose density and primary and secondary endpoints

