6.3.10 Adverse Events

Analyses of AEs will be based on the Safety set. AEs will be coded using Medical Dictionary for Regulatory Activities (MedDRA) Version 17.1.

All AEs will be listed by treatment group, with patient number in addition to type of event (verbatim term, system organ class and preferred term), start and stop day relative to first dose of treatment, seriousness, intensity, action taken, relationship to study drug and outcome of AE. Treatment-emergent status will be flagged in the listing. In addition, corresponding listings of screening AEs, serious AEs (SAEs), AEs leading to discontinuation of study medication, AEs leading to death will be produced.

The total number of AEs will be summarized including the number of patients with at least one AE, the total number of AEs, the number of unique AEs, by seriousness, intensity, action taken, relationship to study drug and by treatment group and in total. The number of AEs per severity (CTCAE) and relation to trial drug will also be included and summarized per treatment group and in total. SAEs will also be summarized separately in a similar manner.

The number of patients and the number of AEs will be tabulated by MedDRA system organ class (SOC) and preferred term in descending order of overall frequency.

AEs occurring during the 4 hours following the Intuvax vaccination will in addition be summarized separately.

Summary statistics of AE will be done by treatment group.

Pre treatment events occurring between first assessment at Screening and first Intuvax dose (for vaccinated patients) and between first assessment at Screening and Nephrectomy (for unvaccinated patients) will be summarized separately.

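### The SAP's partial-date rule assigns January when only the day of a start date is missing, which can move the date back by up to 11 months and flag some on-treatment adverse events as pre-treatment

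*SAP*

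**What the plan says.** SAP 6.6 lists partial dates as recorded but estimates them for calculations, giving AE duration and medication use as examples. Start dates have two branches, one for an unknown month and one for an unknown day. The second opens "If the day is unknown, then" and has two limbs. The first is "If the month and year match the month and year of the first dose date, then impute the day of the first dose date". The second, for every other case, is "Otherwise, assign 'January". The month-unknown branch directly above ends with the same instruction. The corresponding end-date rule is different: "If the day is unknown, then assign the last day of the month".

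Two later provisions in SAP 6.6 bear on this:

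- If the rules do not give the most conservative date, "then the imputed value may be replaced by a date that will lead to a more conservative analysis".
- After imputation, a three-case strategy sorts AEs with incomplete dates into pre-treatment and treatment-emergent. Each case starts from a missing start date, for example "If the start date is missing but the stop date is not missing and is before the day of first study drug administration".

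The imputed dates are used in two places. Under SAP 6.3.10 the AE listing shows start day relative to first dose, and "Treatment-emergent status will be flagged in the listing". The same section summarises separately the events between the first Screening assessment and first Intuvax dose (vaccinated patients) or Nephrectomy (unvaccinated patients). SAP 6.3.9 counts a medication as started before or after Screening by its first start date.

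**The concern.** In the day-unknown branch the month is known, so January is the wrong kind of value. Either it overwrites a recorded month with one that may contradict it, or it leaves the day unfilled and the rule cannot be run. If a programmer follows it literally, the start date moves backwards, never forwards. That is the direction that turns an on-treatment event into a pre-treatment one and a post-Screening medication into a prior one. At stake are the treatment-emergent flag, the relative start day, part of the pre-treatment AE summary, and the before/after-Screening split of medications.

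**Working it through.** The plan states no figure on this point, so there is nothing to reproduce. The check applies the rule as written and compares it with a rule that keeps the recorded month.

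**Inputs.** The start-date rules are those of SAP 6.6. The first Intuvax dose is within 28 days after Screening (Protocol 7.2.1.2). Nephrectomy is within 63 days of Screening (Protocol 7.2.1.4). AEs are recorded from the Screening Visit to the End-of-Study Visit, at 78 ± 2 weeks (Protocol 10.5.2 and 7.2.1.7). The SAP gives no day to go with January, so day 1 is assumed.

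**Step 1: size of the shift.** Shift in months = recorded month − 1. The maximum is 12 − 1 = 11 months. From 1 December back to 1 January is 365 − 31 = 334 days.

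**Step 2: examples (dates invented for illustration).**

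| First dose | Recorded start | Literal rule | Months back | Status under literal rule | Recorded-month rule |
|---|---|---|---|---|---|
| 15 Feb 2017 | Dec 2017 | 1 Jan 2017 | 11 | before first dose | 1 Dec 2017, after first dose |
| 15 Mar 2017 | Jun 2017 | 1 Jan 2017 | 5 | before first dose | 1 Jun 2017, after first dose |
| 15 Nov 2016 | Jun 2017 | 1 Jan 2017 | 5 | after first dose | 1 Jun 2017, after first dose |

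Reclassification therefore needs an event in the same calendar year as the first dose and in a later month. Events in the first-dose month are protected by the first limb. The third example keeps its flag, but its relative start day is still too early by 31 + 28 + 31 + 30 + 31 = 151 days, measured from 1 June.

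**Step 3: how often a day-missing on-treatment event would be reclassified.** All 365 possible first-dose dates in a year were paired with every event day to the end of follow-up, assuming uniform timing of both:

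| Follow-up after first dose (days) | Share moved before first dose, literal rule | Recorded-month rule |
|---|---|---|
| 28 | 42.2% | 0% |
| 84 | 69.8% | 0% |
| 182 | 66.3% | 0% |
| 365 | 45.5% | 0% |
| 518 (78 × 7 − 28) | 32.1% | 0% |

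Short follow-up leaves many events in the protected first-dose month. Long follow-up puts many into a later calendar year, where 1 January falls after first dose. These are shares of day-missing on-treatment events, not of all AEs.

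The 0% follows by logic. An event in a later month than the first dose gets the first day of that month, which is after the dose. An event in the dose month gets the dose date. Where the first day of the recorded month is assigned, the date moves by at most 31 − 1 = 30 days.

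**Step 4: which moved events reach the pre-treatment summary.** The imputed 1 January must fall between Screening and the cut-off for the arm.

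- Vaccine arm: first dose at most 28 days after Screening, so first dose must fall on about 2 to 29 January.
- Control arm: Nephrectomy at most 63 days after Screening, so Nephrectomy must fall between about 2 January and 5 March (1 January + 63 days in a non-leap year).

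In the second example, 15 March − 28 days = 15 February. Screening was therefore no earlier than 15 February, and the January date precedes it. The flag is wrong, but the event does not enter the summary.

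**Step 5: medications.** With Screening on 15 February 2017 and first dose on 15 March 2017, a medication recorded as started in June 2017 becomes 1 January 2017 and is counted as started before Screening.

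**The case against.** The best reply is that this is a copying slip. The fallback repeats the bullet above it, the end-date rule keeps the month, and a sensible programmer would use the first day of the month. That is very likely the intention, but the text is an operative instruction that says something else.

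The second reply is that the override sentence is aimed at this error, since the text after it treats treatment-emergent as the conservative outcome. That is fair, but the sentence is permissive and names no replacement date. SAP 6.2 also says that review of ongoing data in this open-label trial is not blind, so date-by-date repair is weaker than a fixed rule. The three-case strategy does not help either, because a date already imputed is no longer missing.

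The third reply, that the reach is narrow, largely stands:

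- The AE, SAE and severity tables use all AEs in the safety set.
- Listings show the date as recorded, so the true month stays visible.
- A January date before Screening lies outside the AE collection window and could be caught by the checks in SAP 6.2.

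Two stronger readings are tempting and are not supported. A reader might infer that time to treatment failure is shortened, or can end before randomisation. Its definition (before SAP 6.3.8) "will be derived as the date of screening until start date of second line treatment following progression", so the origin is Screening, not randomisation. SAP 6.6 does not mention it, and a start date before progression would contradict the event definition. The general wording of SAP 6.6 could take in second-line start dates, but that is an inference, and the endpoint is not among those in SAP 3.1 and 3.2. A reader might also infer that reported AE and medication durations are inflated. No table of AE or concomitant-medication duration is planned, and SAP 6.3.3 says only that a duration may appear in a listing.

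**Conclusion.** The rule is wrong as written, and nothing else in the SAP reliably corrects it. Followed literally, it moves a start date back by up to 11 months. It can misstate the treatment-emergent flag and relative start day in the AE listing, in some cases the pre-treatment AE summary, and the before/after-Screening classification of medications.

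The practical weight is low. Overall AE, SAE and severity tables and overall survival do not depend on it, and any effect on time to treatment failure is conditional on applying the rule to second-line start dates. The number of day-missing start dates is not given and could be zero. The 32% to 70% range in the working rests on uniform timing and on day 1 for January. It describes how the rule behaves, not how many of this trial's events are affected.

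**What to change.** In the day-unknown branch for start dates in SAP 6.6, replace the fallback with: if month and year differ from those of the first dose, assign the first day of the recorded month. Keep January only for an unknown month, and state the day there (1 January), because that branch also gives none.

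One limit remains. A start in the month of Screening, when that is not the month of first dose, can still be dated up to 30 days early and so before Screening.

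The cost is one corrected line plus the stated day, with no new data and no protocol change. It can go in a SAP revision or, as SAP 6.2 allows for minor clarifications, in the Pre-Analysis Review Form signed before database lock.
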